The study is a two-armed, parallel-group randomized controlled effectiveness trial with a waitlist control comparing a novel parenting intervention, *BeThere*, with waitlist control (control intervention). The trial is unblinded, in that both the study subjects and field workers delivering the intervention will know the treatment allocation. The trial statistician and PI of the study will be blind to treatment allocation until such a point in the primary analysis when this becomes impossible. DMEC reports for the closed sessions will be produced partially blind.

The study is conducted in South Sudan, a country that has suffered through decades of armed conflict. Bor County, located in Jonglei State, experienced extreme levels of violence during the Second Sudanese Civil War and the South Sudanese Civil War. Bor County is primarily home to the Nilotic Dinka tribe and is a region that is vulnerable to floods. It consists of six payams, including Bor Town – the urban center, which is home to a mix of tribes from Jonglei State and South Sudan. In 2014, Bor Town was destroyed, resulting in the displacement of approximately 50,000 people. The five other payams – Kolnyang, Anyidi, Makuach, Baidit, and Jalle – are rural areas. This project takes place in five villages/bomas within Kolnyang, Anyidi, and Makuach: Pariak, Ghoi, Taragok, Tibek, and Lenguat.

The trial sample comprises caregivers living within these five villages who consent to participate and are randomised into the *BeThere* trial. Any non-randomised participants included in the *Bethere* or waitlist control are not part of the trial sample but will be recorded in the database. The randomised trial sample is the Intention to Treat (ITT) population. For the intention to treat analysis, subjects will be analysed according to the treatment group to which they were randomised, regardless of eligibility (inclusion/exclusion) error, post-randomisation withdrawal, and whether the correct study intervention/treatment was received etc.

10. Randomization

Households were randomized to *BeThere* or the waitlist control after caregivers completed the baseline assessment. A block randomization design was used where the total target sample size ($n=960$) was divided equally across the five study communities, resulting in recruitment of 192 caregivers per community allocated to the *BeThere* intervention or waitlist control.

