Randomization followed a participatory procedure successfully implemented in prior RCTs. At baseline, after completing questionnaires, one caregiver per family drew a piece of colored paper (yellow or green) from an opaque bag with equal distribution, ensuring balance across groups. One of the chiefs in each community then flipped a coin to determine which color corresponded to *BeThere* versus waitlist control. This process was repeated in each study community to maintain equal allocation across sites. The two-step method was designed to enhance transparency and community acceptance; previous studies using this approach showed no baseline imbalances and high follow-up rates in both arms.

Within families, a single index child aged 3–14 was randomly selected using a die-rolling procedure, proportionate to the number of eligible children. If the selected child was 7–14 years old, and both caregiver and child provided consent/assent, the child completed their own assessments at baseline, endline, and follow-up. Group assignments and index child selections were recorded in a master list maintained securely in War Child offices, with access restricted to the scientific and research coordinators.

11. Sample size

Sample size calculations were conducted using a joint significance estimator for indirect effects. Assuming a two-sided alpha of 0.05, an intervention–mediator error correlation of 0.2, mediator SD of 0.2, and error SD of 0.5, a sample of 425 caregivers per arm was sufficient to detect a mean difference of 0.4. Allowing for 10% attrition, the study aimed to enroll 960 caregivers (at least 480 families) and 400 index children across 40 intervention groups, providing adequate power to test multiple mediator models. In the end, we enrolled 956 caregivers and 328 index children.

12. Framework

The objective of the study has a superiority hypothesis testing framework. It aims to show the superiority of BeThere relative to the waitlist control condition on primary and secondary outcomes. In addition, through mediation analyses, this study aims to identify the mechanisms through which BeThere exerts an effect on child wellbeing.

13. Statistical interim analyses and stopping guidance

No interim analyses of study outcomes were planned or conducted. The Data Safety Management Committee reviewed adverse events throughout the study implementation and were responsible for determining whether any actions were required to reduce risk to study participants.

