21. Screening data

There were no diagnostic or clinical screening criteria for admission into the study.

22. Eligibility

The study aimed to enroll 960 caregivers and 400 children in Bor Country, South Sudan. Families were randomized to the BeThere intervention or waitlist control with 1:1 allocation and it is possible that more than one caregiver per family participated in the intervention. Randomization at the family-level ensured that caregivers from the same family were allocated to the same study arm. Individuals were eligible for the trial if they were:

- 1) Primary caregivers of children aged 3-14 years;
- 2) fluent in Dinka;
- 3) Living in Pariak, Ghoi, Taragok, Tibek, or Lenguet communities in Bor Country, Jonglei State, South Sudan; and 4) Willing to participate and commit to all nine sessions of BeThere.

For households with more than one caregiver, all caregivers must be willing to participate in order to be included. Individuals were excluded if they were less than 18 years of age, had participated in either a parenting or stress management intervention within the last six months, did not have a child aged 3-14 years, were unable to complete the assessment, were not fluent in Dinka, or were unwilling to give informed consent. One index child per household was randomly selected. If the selected index child was 7-14 years of age, they were also enrolled in the study and completed child-reported assessments at baseline, endline, and follow-up. If the index child was between 3-6 years of age, they did not complete an assessment. However, their caregivers were still enrolled and participated in study assessments. Not all households had more than one caregiver and/or an index child between the age of 7-14 years who agreed to participate.

[figure not shown]
23. Recruitment

Participants were recruited through community-based organizations, chiefs, and existing networks with whom War Child had established relationships. Recruitment methods included flyers, awareness sessions, door-to-door outreach, and word of mouth, and continued until the target of 192 participants per location was reached. Strategies used successfully in the pilot RCT were applied to engage male caregivers, such as scheduling around income-generating activities and tailoring messaging to their interests.

24. Withdrawal and loss to follow-up

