The analyses outlined in this strategy will be pragmatic, based on ITT and will utilize all available follow-up data from all randomised participants. The trial statistician will be blinded to treatment allocation. The main statistical analyses will establish the effectiveness of BeThere over waitlist control by comparing the mean difference of total parenting score at endline post randomization (see appendix).

Primary outcome

The primary outcome is the total score of the parenting scale at endline. We will compare randomized groups at endline and follow-up adjusted for baseline total score of parenting scale and account for hierarchical clustering of caregivers at the level of household. Specifically, we will fit a three-level random intercept linear regression model considering observations from endline and follow up at level 1, household at level 2 and community at level 3. The model will include the total score parenting scale at endline and follow up as the outcome variables with treatment group, baseline rate of parenting total score as explanatory variables. A time by treatment interaction will be included to allow the effect to differ at each time point (endline, follow up).

Secondary outcomes

Secondary outcomes as listed will be assessed with a similar methodology for the primary outcomes, using generalized linear mixed models with the appropriate link function/distribution. Normal outcomes will use an identity link function, binary variables would use a logit link function, and Poisson (count) variables would use a log link function. We will use all available time points in the model and extract differences at endline and follow up post-randomisation. All the questionnaires to be used have validated methods of scoring.

Method for handling non-compliance

In addition to the primary intention-to-treat analysis the effect of actually receiving treatment as defined in the protocol will also be estimated using a per-protocol analysis (PP). The PP analysis will remove data of those who:
attended fewer than seven sessions and any participant who did not complete all study assessments.

Planned sensitivity analysis

As a sensitivity analysis, we will replicate the effectiveness models excluding Community #1: Tibek due to implementation issues and delays. We will conduct subgroup analyses for the effectiveness models

stratified by gender of the caregiver, number of caregivers in the household (1 vs. 2), and child age (3-7 years vs. 8-14 years).

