Mediation Analyses

Estimate indirect effect of BeThere intervention on child wellbeing via caregiver wellbeing, caregiver distress, caregiver stress, and parenting.

Single mediator models. We will test for the effect of the BeThere intervention on each one of the multiple continuous mediators with the use of linear regression models. We chose a priori a p-value of lower than 0.15 to select the appropriate mediators to include in our final mediation analysis. We will test independence by examining partial correlations between our mediators after accounting for treatment allocation.

Full Structural Model. We will estimate a parametric structural equation model (sem package in Stata version 16.0 [StataCorp]) to estimate the total effect, the natural indirect effects (NIE), and natural direct effects (NDE) of Bethere on child wellbeing via caregiver wellbeing, caregiver distress, caregiver stress, and parenting. The NDE represented the effect of BeThere on Child Psychosocial Wellbeing (caregiver report) that was independent of caregiver wellbeing, caregiver distress, caregiver stress, and parenting. The NIE represents the proportion of BeThere intervention that could be explained by its effect on changes in caregiver wellbeing, caregiver distress, caregiver stress, and parenting. To quantify the magnitude of mediation, the study estimated the proportion of the effect mediated by caregiver wellbeing, caregiver distress, caregiver stress, and parenting ($NIE/[NDE + NIE]$). All analyses will be estimated using bootstrapping (500 replications) to recover the correct SEs for direct and indirect effects. Results are presented as coefficients and 95% confidence intervals (see appendix).

[figure not shown]
[figure not shown]

Figure 6 Primary mediation pathways

To assess the effect of group cohesion among beneficiaries in the BeThere intervention group on caregiver wellbeing and distress

First, we will examine the correlations among midline and endline group cohesion values with endline and follow-up caregiver wellbeing, stress, and distress.

We will use a structural equation model (SEM) to estimate the indirect effect of the BeThere intervention on caregiver outcomes through group cohesion. The model will specify caregiver wellbeing, caregiver stress, and caregiver distress at endline and follow-up as the outcomes using a similar method to that described above.

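### The mediation models for primary Objective 3 name no community term, so community differences shared by mediators and child wellbeing can appear as mediation

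*SAP*

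**What the plan says.** Section 10 (Randomization) has the target of 960 caregivers "divided equally across the five study communities", 192 in each. Of the paper draw and coin flip it says: "This process was repeated in each study community to maintain equal allocation across sites". Section 22 gives the unit: "Families were randomized to the BeThere intervention or waitlist control with 1:1 allocation".

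Section 27a (Primary outcome) carries the communities into the effectiveness model, with "household at level 2 and community at level 3". Secondary outcomes follow a similar method.

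Section 27a (Mediation Analyses) is specified differently:

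- Single-mediator step: "We will test for the effect of the BeThere intervention on each one of the multiple continuous mediators with the use of linear regression models".
- Check of mediator independence: "examining partial correlations between our mediators after accounting for treatment allocation".
- Full model: "We will estimate a parametric structural equation model (sem package in Stata version 16.0 [StataCorp]) to estimate the total effect", plus natural direct and indirect effects, with 500 bootstrap replications and no stated resampling unit.
- The group-cohesion SEM takes over a similar method.

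No community, household or baseline covariate is named in any of these. The community variable (int_location) is in the dataset in Appendix 1 but is assigned to no mediation model.

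**The concern.** The indirect effect is the product of two paths. The first, BeThere to mediator (a), is randomised, and 1:1 allocation inside each community keeps it and the total effect free of community bias. The second, mediator to child wellbeing (b), is observational even in a randomised trial. If some communities have both less distressed caregivers and better-off children for reasons unrelated to the pathway, a model that pools the communities attributes that pattern to b. With only five communities, a chance alignment is also possible when the two sets of differences are unrelated, and standard errors that treat caregivers as independent do not allow for it.

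Objective 3 is one of the three primary objectives, and these estimates form the second planned manuscript. A mechanism could be declared, or a proportion mediated inflated, because of which communities the families lived in.

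**Working it through.** **Inputs from the SAP.** Five communities of 192, 5 × 192 = 960; 956 caregivers enrolled; 10% attrition allowed for, 956 × 0.9 ≈ 860. The SAP gives no community ICC and no false-positive figure for mediation, so there is no figure of its own to reproduce here.

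**Assumptions.** Standardised scales; BeThere effect on the mediator a = 0.3 SD; true b = 0; the same community ICC for mediator and outcome; r = correlation of the two community effects. Mediation is declared by joint significance of a and b at two-sided 5%, a stand-in for the bootstrap interval.

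**Average bias.** Without a community term, the mean of the estimated b is about r × √(ICC_M × ICC_Y) × 4/5. The factor 4/5 arises because five community effects vary about their own mean.

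- ICC 0.05, r = 0.5: 0.5 × 0.05 × 0.8 = 0.020 (simulated 0.021).
- ICC 0.10, r = 0.5: 0.5 × 0.10 × 0.8 = 0.040 (simulated 0.043).
- ICC 0.10, r = 1: 1 × 0.10 × 0.8 = 0.080 (simulated 0.080).

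The spurious indirect effect is 0.3 times b, so at most 0.3 × 0.080 = 0.024 SD here.

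**Chance alignment when r = 0.** The bias averages zero, but the community effects add an SD of about 0.4 × ICC to b (√4/5 = 0.4). The nominal standard error with 955 caregivers is 1/√955 = 0.032. At ICC 0.10 the true SD is √(0.032² + 0.040²) ≈ 0.051 (simulated 0.050 without indicators, 0.032 with them). The reported standard error is therefore too small.

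**False-mediation rate.** Ranges run from r = 0 to r = 0.5. The first simulation has five communities of 191 and 3,000 runs; the second has 850 caregivers and 1,500 runs.

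| ICC | 955 caregivers, no community | 850 caregivers, no community | Community indicators, both |
|---|---|---|---|
| 0.01 | 5.2-5.8% | 6.2-7.4% | about 5-6% |
| 0.02 | 5.0-6.2% | not run | about 5% |
| 0.05 | 9.7-13.9% | 8.5-13.9% | about 5-6% |
| 0.10 | 19.0-32.0% | 18.0-31.3% | about 5-6% |

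With r = 1 the rate without a community term was 24.2% at ICC 0.05 and 54.0% at ICC 0.10 (850 caregivers). With a = 0 it stayed below 2% throughout, because joint significance then fails on the first path.

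**Would baseline scores be enough?** Baseline mediator and outcome scores were added, with autocorrelation 0.5. If the community effect is the same at baseline and endline, the rate without indicators falls to 5.5-7.5% at ICC 0.05-0.10. If the community shift arises after baseline, the rate is 13-20% at ICC 0.05 and 28-41% at ICC 0.10, against 4-7% with indicators.

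**The case against.** The strongest reply is that the size rests wholly on an assumed ICC. The sites are five villages in three rural payams of one county, and all caregivers must be fluent in Dinka. The ICC may be 0.01-0.02, where nothing visible happens. Even at ICC 0.10 the average spurious indirect effect is small. Community is also only one of several covariates that the mediation section does not name. All of this stands. It limits the size of the problem but does not justify leaving out a variable that the effectiveness model already uses.

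Four stronger readings are tempting, and the document does not support them.

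- *That separate randomisation creates the bias.* It does not. Allocation within community protects the a-paths and the total effect. The bias comes from community as a possible common cause on the unrandomised paths and would be the same without stratification.
- *That the mediation table shell shows community is excluded.* The outcome shell has no community row either, although that model includes community. The mediation figures are also not available here, so a covariate drawn only there cannot be ruled out.
- *That the implementation problems in Tibek demonstrate confounding.* Weaker delivery is more directly a difference in treatment effect between communities. In a simulation with no BeThere effect in one community and effects of 0.375 SD (mediator) and 0.25 SD (outcome) in the other four, false mediation was 5.3% without and 5.2% with indicators.
- *That the bootstrap resamples individuals.* The resampling unit is simply not stated.

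**Conclusion.** The point holds as an omission that should be corrected before the mediation analysis is run. The SAP writes out both sets of models, includes community in one and names it nowhere in the other, and the unprotected paths carry a primary objective.

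The effect is negligible at a community ICC of 0.01-0.02. At ICC 0.05 the nominal 5% rises to about 9-14%, and at ICC 0.10 to about 19-32%. These figures assume a true b of zero, a = 0.3 SD, equal ICCs and r between 0 and 0.5. They need a non-zero effect of BeThere on the mediator. Nothing in the document shows which ICC applies, so a reader should not infer that false mediation will occur, only that the model as written does not guard against it. The total effect is not in question.

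**What to change.** In section 27a, Mediation Analyses:

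1. Add four community indicators (from int_location, five levels) to each single-mediator regression and to every mediator and outcome equation of the SEM, including the group-cohesion SEM.
2. Condition the partial correlations among mediators on community as well as allocation.
3. State that the bootstrap resamples households within community. Resampling individuals would break up two-caregiver households, which were randomised together.

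Indicators are preferable to a random intercept here: they remove all between-community differences from the b-paths, and five communities are few for estimating a variance.

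The cost is a few sentences of text and four degrees of freedom per equation, out of about 860 caregivers if the planned 10% attrition occurs. The variable is already in the dataset. In the simulations the indicators cost no visible precision. They adjust for community main effects only. They do not address differences in the BeThere effect between communities, or other mediator-outcome confounders such as baseline scores.

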14. Timing of final analysis

All analyses will be conducted after completion of data collection for the trial. The statistician and PI will be masked to study condition during data collection, cleaning, and the primary effectiveness analyses. Secondary analyses examining mediators that relate to intervention group characteristics (e.g., BeThere Mechanism of Action, Group Cohesion) or require analysis of intervention midline assessment data will be conducted after effectiveness analyses are finalized to preserve masking.

15. Timing of outcome assessments

Data used for this study will be collected by research assistants at baseline, midline (BeThere session 5), endline (within 2-3 weeks following session 9 or approximately 10-12 weeks post-enrollment), and follow-up (12 weeks after completion of the final session or approximately 22 weeks post-enrollment). The midline assessment was only administered to the experimental (i.e., BeThere) group and not to the waitlist control group.

SECTION 4: STATISTICAL PRINCIPLES

16. Level of statistical significance

A significance level of $\alpha=0.05$ will be applied.

17. Adjustments for multiplicity

We do not plan to adjust for multiple testing.

18. Confidence intervals

Results will be presented as coefficients and 95% CIs.

19. Adherence and protocol deviations

Participant adherence to the intervention will be measured using intervention session attendance records. Completion of the intervention will be defined as having attended seven or more sessions. We will report the mean (SD) and median (IQR) number of sessions attended in the BeThere group.

Facilitator fidelity to the intervention will be measured using a fidelity checklist. We will report the mean (SD) and median (IQR) scores on the fidelity checklist as an indicator of trial implementation quality.

Any major deviations from the protocol will be reported in the main outcomes paper.

20. Analysis populations

The primary analysis will be conducted on the intent-to-treat sample, meaning that all participants will be included and analyzed as randomized. No enrolled participants were excluded from the main analytic sample. We will also conduct a per protocol analysis including waitlist control participants who completed all assessments and did not participate in any BeThere intervention components and only BeThere intervention participants who completed seven or more intervention sessions and did not drop out of the study.

SECTION 5: TRIAL POPULATION

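### The confidence interval for indirect effects is left unnamed and worded as SE-based. That form can lose power against the joint-significance sizing when both paths are weak; a percentile bootstrap interval should be named.

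*SAP*

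**What the plan says.** Section 8 lists estimation of the indirect effect on child wellbeing, through caregiver wellbeing, distress, stress and parenting, as the third primary objective. Section 2 makes the mediators the subject of one of two planned papers.

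On sizing, section 11 says "Sample size calculations were conducted using a joint significance estimator for indirect effects". Its inputs are given as "Assuming a two-sided alpha of 0.05, an intervention–mediator error correlation of 0.2, mediator SD of 0.2, and error SD of 0.5", and it concludes that "a sample of 425 caregivers per arm was sufficient to detect a mean difference of 0.4". No power is stated.

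On analysis, section 27a (Mediation Analyses, Full Structural Model) says "All analyses will be estimated using bootstrapping (500 replications) to recover the correct SEs for direct and indirect effects". The next sentence announces coefficients with 95% confidence intervals, and section 18 says only "Results will be presented as coefficients and 95% CIs". Neither place, nor the mediation table shell in Appendix 1, says whether the intervals are normal-based, percentile or bias-corrected. Joint significance is not mentioned again after section 11. The group-cohesion SEM is to follow a similar method.

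**The concern.** An indirect effect is a product a×b, where a is the intervention-to-mediator path and b the mediator-to-outcome path. Unless at least one path is estimated precisely relative to its size, the product has a skewed sampling distribution. An interval of the form estimate ± 1.96 SE is symmetric whatever the shape, and it tends to cover zero even when both paths are individually significant. Joint significance asks only that both paths be significant, so it does not pay this price.

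SE recovery is the only purpose section 27a gives the bootstrap, so the normal-based interval is its natural reading. On that reading, a primary objective is analysed with a less powerful method than the one used to size the trial. A mediator with two modest but real paths could have an interval that includes zero because of how the interval was built. The proportion mediated, NIE/(NDE + NIE), is a ratio whose denominator may be near zero, so a symmetric interval suits it poorly too.

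**Working it through.** **Inputs from the SAP.** Section 11: joint significance, two-sided alpha 0.05, correlation 0.2, mediator SD 0.2, error SD 0.5, effect 0.4, 425 per arm (850 in total), 10% attrition, at least 480 families, and 956 caregivers enrolled. Section 27a: 500 bootstrap replications.

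**Assumptions.** The 0.4 is read as the mediator-outcome coefficient b, and 0.2 as the intervention-mediator correlation ρ. Units are independent.

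**1. The plan's own figure.** The regression-mediation formula is N = (z for alpha + z for power)² × SDe² / (b² × SDm² × (1 − ρ²)). The denominator is 0.16 × 0.04 × 0.96 = 0.006144.
- 80% power: N = 319 in total.
- 90% power: N = (1.960 + 1.282)² × 0.25 / 0.006144 = 428 in total.

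So 425 is approached only as a total at 90% power. Read as 425 per arm (850 in total), power is 99.5%. Because no power is stated, both sizes are carried forward.

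**2. How the two methods differ.** In units of each path's own SE, joint significance needs |z_a| > 1.96 and |z_b| > 1.96. The bootstrap-SE interval excludes zero when |z_a z_b| / √(z_a² + z_b² + 1) > 1.96. With both estimates at 2.5, this is 6.25 / √13.5 = 1.70, so both paths are significant but the interval includes zero. With equal paths, the condition z⁴ > 3.8416 × (2z² + 1) gives z above about 2.86.

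**3. At section 11's inputs.** z_a = ρ√(N/(1 − ρ²)) and z_b = b × SDm × √(N(1 − ρ²)) / SDe. Power from at least 400,000 draws:

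| Independent units | z_a | z_b | Joint | SE-based | Loss (points) |
|---|---|---|---|---|---|
| 850 (425 per arm) | 5.95 | 4.57 | 99.5% | 99.2% | 0.3 |
| 480 (minimum families) | 4.47 | 3.43 | 92.4% | 85.2% | 7.2 |
| 425 (read as the total) | 4.21 | 3.23 | 88.8% | 78.1% | 10.8 |

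Over a grid of path strengths, the largest loss was about 27 points, at z_a and z_b near 2.5 to 2.75. Losses of 20 or more needed two similarly weak paths and joint power of about 81% or less.

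**4. Modest paths, one mediator.** Here n = 860 (956 less 10%), with independent normal errors, 500 replications and 1,000 simulated trials. The effect sizes d (intervention on mediator) and r (partial correlation of mediator with outcome) are assumed; the SAP gives none.

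| d, r | Joint | SE-based CI | Percentile CI |
|---|---|---|---|
| 0.15, 0.075 | 37.9% | 13.2% | 34.7% |
| 0.20, 0.10 | 69.7% | 43.7% | 67.8% |
| 0.20, 0.15 | 80.4% | 70.1% | 81.0% |
| 0.20, 0.30 | 83.3% | 81.8% | 84.4% |
| 0, 0.30 (null) | 4.4% | 4.3% | 4.9% |
| 0, 0 (null) | 0.1% | 0.0% | 0.1% |

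At d = 0.20, r = 0.10 the paths have z_a = 0.20 × √860 / 2 = 2.93 and z_b = 0.10 × √860 / √0.99 = 2.95, close to the worst region. The percentile interval comes from the same resamples and recovers nearly all of the joint-test power.

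**5. Four mediators, as section 27a plans.** Same n and replications.
- One mediator's own indirect effect, d = 0.20, r = 0.10 (200 trials): about 36% SE-based against 61% percentile, a 25-point loss.
- NIE summed over four equally active mediators, d = 0.20, r = 0.10 (400 trials): 100% against 100%, 97.5% against 97.8%, and 94.8% against 95.3%, at mediator correlations 0, 0.3 and 0.5.
- The same at d = 0.15, r = 0.075: 89% against 92%, 77% against 80%, and 72% against 74%.
- Summed NIE with only one mediator active: a loss of about 12 points.

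**The case against.** The SAP never writes estimate ± 1.96 SE. Percentile limits could be taken from the same 500 replicates, so the normal-based interval is an inference. This stands: what the document shows is an unnamed interval and wording that points to the weaker form.

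A reader might infer that mediation power falls by 20 points or more in general, or that the sample size is invalidated. The documents do not support that. At section 11's inputs with 850 independent caregivers the loss is 0.3 points, and the larger losses rest on effect sizes that the SAP does not give. The summed NIE, which section 27a defines, is a sum of products and so closer to normal; with all four mediators active it loses little. The large loss belongs to the mediator-specific indirect effects, for which the table shell has a column, and a smaller one to a summed NIE with few active mediators.

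Two further inferences fail. Near-zero rejection when both paths are null is no special fault of the SE-based interval, since joint significance and the percentile interval behave alike there. And the SAP has no rule that dismisses a mediator when its interval includes zero; the objective is to estimate.

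Against this, the mild case cannot be taken for granted. Caregivers are clustered in households, correlated mediators can weaken each partial b path, and mediators may enter the model at p < 0.15. Leaving the interval open also permits a choice between methods that can disagree.

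**Conclusion.** The point holds as a conditional one. The SAP does not name the interval for indirect effects of a primary objective, and its wording suggests a form less powerful than the method used for sizing. The cost runs from negligible at section 11's inputs and 850 independent units to about 25 points for a mediator-specific effect with two modest paths. The intermediate cases are 7 to 11 points at 425 to 480 independent units, and 0 to 12 points for the summed NIE.

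These figures rest on the stated reading of section 11, on assumed effect sizes in the modest-path cases, and on simulations with independent errors and no household clustering. The error is in the conservative direction: real indirect effects may be missed, but no false ones are created. The change is worth making because a better interval is available from the same resamples.

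**What to change.** In section 27a, replace the SE sentence with: '95% CIs for the indirect, direct and total effects and for NIE/(NDE + NIE) will be percentile bootstrap intervals; bootstrap SEs are descriptive.' State that the same applies to the group-cohesion SEM.

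More than 500 replications is advisable to stabilise the tail percentiles, but it is not the source of the gain: the percentile results above used 500. Data, models and participants are unchanged. The cost is one sentence and slightly more computing time.
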